## Secondary Objectives:

- 1. To compare the change in percent mammographic density from Baseline to the Week 52 mammogram in women applying 8 mg 4-OHT vs. placebo, using two breast density measurement methods (Cumulus versus Volpara).
- 2. To compare the percentage of women who underwent a change in BI-RADS category when comparing pre-and post-treatment measurements for recipients of 4-OHT and placebo.
- 3. To compare the percentage of women with a  $\pm$  10% absolute decrease in quantitative mammographic density (Cumulus) between baseline and 52 weeks, when comparing between the recipients of 4-OHT and placebo.
- 4. To describe the symptoms assessed by laboratory toxicity assessments complete blood count (CBC) w/diff, blood chemistry, coagulation factors, lipid panel, liver function tests, sex hormone binding globulin (SHBG), and bone biomarkers.
- 5. To determine the safety and tolerability of 8 mg/day of 4-OHT after 52 weeks of administration to the breasts such as AE collection, effects on menstrual cycle, and laboratory values.
- 6. To determine whether 8 mg/day of 4-OHT will disrupt the menstrual cycle of premenopausal women.
- To determine the plasma concentration of the E and Z isomers of 4-OHT after 13, 26, 52, 78, and 104 weeks of application of 4 mL BHR-700 gel to the breasts.

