#### 5.3 Dose Reduction

If a subject experiences toxicity that may make her want to stop taking study drug, the dose of study drug will be reduced by 50%, to 2 mg (1 pump actuation) to each breast. The reduced dose will be maintained for the duration of the study.

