#### 8.0 ASSESSMENTS OF SAFETY

#### 8.1 Adverse Event Collection and Reporting

#### • Adverse Event Collection

AEs will be captured for the duration of the study. The reporting period begins with the first dose of study drug (Study Day 1) and ends at Week 52 and Week 104. The Adverse Events eCRF must be completed for all reported AEs and SAEs.

For this study, an AE is defined as: "Any untoward medical occurrence in a patient or clinical investigation subject administered a pharmaceutical product and which does not necessarily have a causal relationship with this treatment." This includes any newly occurring event or previous condition that has increased in severity or frequency since the administration of study drug.

AEs may also be reported spontaneously at any time. Details of any adverse or unexpected events, signs, and symptoms will be collected including details of onset, resolution, frequency, severity (as defined below), seriousness, relationship to the drug, effect on the study drug, treatments administered, and outcome. Any AE will be followed, whenever possible, until it returns to the baseline condition or becomes stable with no further change expected.

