#### 1.2 Design

This is a multi-center, randomized, double-blind, placebo-controlled study in women identified as having dense breast tissue upon screening mammography.

Subjects who give informed consent will have screening evaluations, including hormone measures of FSH, Estradiol and Estrone to determine menopausal state. Those subjects meeting entry criteria, will be stratified, based on their hormone levels, into pre/peri and post menopause groups and randomized within those groups 2:1 to receive either 8 mg/day (4 mg/breast) BHR-700 gel or placebo for up to 52 weeks. At the Principal Investigator's (PI) discretion, subjects may be allowed to reduce the dose to 4 mg/day (2 mg/breast) in cases of intolerance.

Subjects will apply the gel to both breasts once per day. The first dose will be applied under the supervision of the PI/designee. Subsequent doses will be self-administered daily by the subject until she has completed 52 weeks of study drug administration. Study drug compliance will be checked at each study visit. Subjects will be asked to capture daily gel administration in a diary and drug canisters will be weighed on release to the subject and on return. The canister weight will be recorded in grams. If the study drug is discontinued or interrupted, the reason(s) will be recorded. During treatment period, subjects will be evaluated at Day 1 and every 13 weeks (±2 weeks) thereafter.

A planned sample size of 330 women, identified as having dense breast tissue upon screening mammography, will be randomized to receive either BHR-700 gel or placebo (at 2:1 ratio). Considering an attrition rate of approximately 15%, it is expected to have 272 evaluable women (4-OHT: 181 & Placebo: 91) who will have both baseline and 52 week measurements of percent mammographic density (MD) of the breast.

Subjects who complete the double-blind phase of the study will be offered entry into an open-label follow-up period for an additional 52 weeks.

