#### Adverse Events

- All adverse events (AE) will be summarized with MedDRA primary system organ class (SOC) and preferred term.
- Summary tables of severe AEs, SAEs and study drug related AEs will also be provided.
- Listings of all AE, serious adverse events (SAE), and severe AEs will be provided.

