# 4.2 Listings to be Included in the Clinical Study Report

# 4.2.1 Listings of subject information

- 1. Listing [LDS01a] Discontinued Subjects (Blinded Phase) ITT Population
- 2. Listing [LDM01a] Demographic Characteristics (Blinded Phase) ITT Population
- 3. Listing [LRN01a] Randomization (Blinded Phase) ITT Population
- 4. Listing [LMH01a] General Medical History ITT Population
- 5. Listing [LMH02a] Special Medical History (Breast Cancer) ITT Population
- 6. Listing [LMH02a] Menstrual History ITT Population
- 7. Listing [LCM01a] Prior Medications and Treatments (Blinded Phase) ITT Population
- 8. Listing [LCM02a] Concomitant Medications and Treatments (Blinded Phase) ITT Population
- 9. Listing [LPD01a] Protocol Deviations (Blinded Phase) ITT Population

- 10. Listing [LPD02a] Protocol Deviations Lead to Exclusion from PP Population (Blinded Phase) ITT Population
- 11. Listing [LSD01a] Study Drug Compliance (Blinded Phase) ITT Population

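### By SAP text and output titles, no planned summary counts dose reductions for intolerance or the adverse events behind them, so tolerability of 8 mg/day is only partly reported

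*SAP*

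**What the plan says.** Secondary objective 5 (Protocol 3.0) is "To determine the safety and tolerability of 8 mg/day of 4-OHT after 52 weeks of administration to the breasts". It names AE collection, menstrual effects and laboratory values as examples of the evidence.

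Protocol 5.3 deals with a woman whose toxicity might lead her to stop: "the dose of study drug will be reduced by 50%, to 2 mg (1 pump actuation) to each breast". It adds: "The reduced dose will be maintained for the duration of the study". Protocol 6.5 repeats the rule. SAP 1.2 words it as an option at the investigator's discretion: "subjects may be allowed to reduce the dose to 4 mg/day (2 mg/breast) in cases of intolerance". The automatic and discretionary wordings should be reconciled, but the point below holds under either.

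Protocol 8.1 lists among the details collected for each AE "relationship to the drug, effect on the study drug, treatments administered, and outcome".

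SAP 3.3.1 plans a summary of all AEs by system organ class and preferred term, and then: "Summary tables of severe AEs, SAEs and study drug related AEs will also be provided". SAP 3.1 presents summaries by treatment group and time point. The listed outputs closest to tolerability are the disposition tables, "Listing [LDS01a] Discontinued Subjects (Blinded Phase) ITT Population" with its open-label counterpart, and study drug compliance. Compliance (SAP 3.2 and 3.7) is the gel weight used divided by 3.52 g times the number of days. It is set to missing for any woman who did not return all her canisters.

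**The concern.** The protocol gives intolerance of 8 mg/day two ways out: stopping, or continuing on half the dose. The SAP lists women who take the first. By its text and titles it never counts those who take the second. The proportion unable to stay on the starting dose is a direct measure of tolerability, and half of that measure is missing.

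This matters more than usual here for two reasons. After early termination, SAP 3.8 limits the study report to a brief one centred on safety and PK/PD, so tolerability is one of its main products. And the earlier clinical doses listed in Protocol 2.2 end at 4 mg/day, with 8 mg/day justified by extrapolation from them. A conclusion on 8 mg/day that does not say how many women moved down to 4 mg/day leaves out what a reader of this trial would most want to know.

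**Working it through.** **1. Output titles.** SAP 4.1 and 5.1 number tables 1 to 24 and 25 to 39, which makes 39. SAP 4.2 and 5.2 number listings 1 to 27 and 28 to 42, which makes 42. None of the titles refers to dose reduction, dose modification, exposure, AEs leading to a change or stop of study drug, or dose at AE onset. The text of SAP 3.3.1 adds nothing on these.

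**2. What happens to the triggering AE.** It starts while the woman is on 8 mg/day. The tables count subjects with an event by treatment group, so it remains in the active arm whatever she does next. Only events that would have occurred later at full dose can be lost.

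**3. Compliance, starting from the plan's own figure.** Inputs from SAP 3.2: 4 actuations of 1 mL a day and a gel density of 0.88 g/mL.
- Full dose: 4 × 0.88 = 3.52 g/day, which reproduces the SAP's figure.
- Reduced dose (1 actuation per breast, so 2 a day): 2 × 0.88 = 1.76 g/day.
- Compliance of a woman who follows the reduced dose perfectly: 1.76 / 3.52 = 50%.
- SAP 3.7 counts days as current visit minus last visit plus 1. Over a 91-day interval this gives (91 × 1.76) / (92 × 3.52) = 160.16 / 323.84 = 49.5%.
- Reduction at day 45 of 91: (45 × 3.52 + 46 × 1.76) / (91 × 3.52) = 239.36 / 320.32 = 74.7%, or 73.9% with 92 days in the denominator.
- Blinded-phase average over four visits, ignoring the extra day, for a reduction after 0, 1, 2 or 3 intervals: 50%, 62.5%, 75% or 87.5%.

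A woman assigned the full dose who misses half her applications also uses 1.76 g/day on average and also scores 50%. The formula cannot separate the two.

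**4. Other limits of compliance as a substitute.** It is missing when any canister is not returned. The open-label phase has a compliance listing but no compliance table.

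**5. Possible size.** The documents give no reduction rate, so the rates here are assumptions. Planned active arm: 330 × 2/3 = 220.
- 5%, 10% or 20% reducing: 11, 22 or 44 women.
- Share of active-arm time at 4 mg/day, for a proportion r reducing at week w with everyone followed to week 52: r × (52 − w) / 52. The low end is 0.05 × 26/52 = 2.5% (week 26); the high end is 0.20 × 48/52 = 18.5% (week 4).

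These use planning numbers. SAP 1.3 reports fewer subjects and shorter treatment for many of them.

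**The case against.** A reader might infer that women who reduce are displayed as tolerating 8 mg/day, and that objective 5 goes unanswered. The documents do not support either reading. The AEs that prompt a reduction stay in the active-arm tables by term, severity, seriousness and relatedness. Against the fixed denominator these women show as falling well short of full-dose use. Objective 5 cites AEs and laboratory values among its means, and both are summarised by arm. What remains is that reduction is hidden and mixed with missed doses.

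It is also tempting to add an assumed reduction rate to the planned 15% attrition and call the sum failure to stay on 8 mg/day. That does not work. The 15% is all-cause attrition used to reach the number of women with evaluable density measurements, in a study that then ended early.

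Three further objections are fair.
- The shells are an attachment that is not visible. The overall AE table or the AE listings may carry an action-taken item, and disposition may give reasons for stopping. This limits the finding to SAP text and titles. A column in a listing would still not be a prespecified count.
- The data may not support everything. Protocol 8.1 collects each AE's effect on study drug, but Protocol 6.8 records reasons for interruption or discontinuation and does not mention reduction. No dated dose-change field is visible, so time to reduction and dose at onset may not be derivable for every woman.
- The report is brief and descriptive. That argues for a small addition, not against one.

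**Conclusion.** The point holds as a gap in reporting. By SAP text and titles, women who moved to half dose for intolerance are not counted, nor are the AEs that led to reduction or discontinuation. The one output that reflects the lower dose presents it as about 50% compliance after a full interval, indistinguishable from missed doses. Objective 5 is answered incompletely: the by-arm tables describe a regimen that starts at 8 mg/day with reduction allowed, without saying how often reduction was used.

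The size is unknown. The figure of 11 to 44 women rests on an assumed 5% to 20% rate and the planned 220 active women; the actual number depends on the lower enrolment. Any lowering of AE percentages through time spent at half dose also assumes that AEs are dose-related, and it affects only events after the reduction. Sample size, power and significance level are untouched. This is a cheap improvement to what a safety-focused report can conclude about 8 mg/day.

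**What to change.** In SAP 3.3.1, 4.1.2 and 4.2.2, and the open-label equivalents in section 5, add by arm:
- n (%) of women with a dose reduction;
- AEs leading to reduction and, separately, AEs leading to discontinuation, taken from the collected effect on study drug;
- a combined count of women who reduced or stopped because of an AE. Stops due to study termination or other reasons must be excluded, since counting them would present the sponsor's decision as intolerance;
- time to reduction and a listing of dose changes, where dates are recorded.

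Calculate compliance against the dose assigned at the time. AEs by dose at onset should be at most a descriptive supplement with person-time, because women who reduce are self-selected and exposure differs between the two doses. The by-arm tables stay primary. Word the objective 5 conclusion as tolerability of a regimen starting at 8 mg/day with reduction allowed.

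The cost is SAP wording and a little more programming, and a tolerability figure that may look less favourable. The counts use information the protocol already collects on AEs; the timing items depend on whether dose-change dates were captured.

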#### Laboratory Tests

• Laboratory data (haematology and blood chemistry) will be summarized for baseline, post baseline, and change from baseline.

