## 8.5 Laboratory Tests

Laboratory tests (hematology and blood chemistry) will be performed by a central laboratory. Laboratory tests will be performed at screening, at pre-dose, at Week 26 and Week 52. For those subjects who have elected to continue open-label treatment for a further 52 weeks, laboratory tests will also be performed at Week 78 and Week 104. The Investigator will assess all abnormal lab values for clinical significance; if categorized as AEs, they will be collected and recorded similarly to other AEs. All clinically significant abnormal lab values will be followed until resolution. If resolution is not seen, a justification as to the cause for such an abnormality, such as due to an underlying pre-existing condition, associated co-morbidity, etc., will be recorded.

The following laboratory assessments will be performed for this study: Hematology, Blood Chemistry, Coagulation factors, Hormones, and Bone biomarkers.

Any residual biological samples will be destroyed after test results are confirmed by the respective testing laboratory. No samples will be retained for future testing.

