#### 2.2.2 Secondary Endpoints

- 1 The percentage reduction in breast density at Week 52 using two breast density measurement methods (Cumulus versus Volpara).
- 2 The percentage of women who underwent a change in BI-RADS category when comparing pre-and post-treatment measurements.
- 3 The percentage of women with a ± 10% absolute decrease in quantitative mammographic density (Cumulus) between baseline and 52 weeks,
- 4 Change in serum concentration of: cholesterol, triglycerides, high-density lipoprotein (HDL), and low-density lipoprotein (LDL).
- 5 Change in serum concentration of sex hormone binding globulin (SHBG).
- 6 Change in serum concentration of Protein C-activity, Protein S-activity, Antithrombin 111 antigen, and Activated Protein C resistance (APCR).
- 7 Change in serum concentration of select bone biomarkers CTx and BSAP.
- 8 Incidence and severity of AEs and laboratory values.
- 9 The menstrual cycle of premenopausal women.
- 10 Pharmacokinetic (PK) plasma concentration of the E and Z isomers of 4-OHT after 13, 26, 52, 78, and 104 weeks of application of 4 mL BHR-700 gel to the breasts.

The secondary endpoints are for both blind and open-label treatment phases.

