# 3. STATISTICAL METHODS

#### 3.1 General

All data will be analyzed using the Statistical Analysis System (SAS®; Version 9.2 or higher).

Safety and efficacy data will be summarized and presented by treatment group and time point in summary tables. Continuous variables will be presented by descriptive statistics: n, mean, standard deviation, median, minimum, and maximum. Categorical variables will be tabulated by frequency count and percentage.

When the actual treatment received by a subject is different from the randomized treatment assigned, the subject will be analyzed per the randomized treatment for the efficacy parameters (using the ITT population); while the subject will be analyzed per actual treatment that was taken for the safety parameters (using the safety population).

Where appropriate, all statistical tests will be two-sided hypothesis tests performed at the 5% level of significance for main effects and all confidence intervals will be two-sided 95% confidence intervals.

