#### Vital sign and Physical Exam

• Vital sign and physical exam abnormalities will be summarized. The data listings of individual abnormalities will be provided.

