#### Normal Ranges for Vital Signs

Vital Signs (unit)	Lower Limit	Upper Limit
Systolic BP (mmHg)	<90	>120
Diastolic BP (mmHg)	<60	>80
Pulse Rate (bpm)	<60	>100
Respiration Rate (bmp)	<12	>18
Body Temperature (F)	<98	>99.1

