# 4.1.2 Summary of safety endpoints

- 9. Table [TAE01a] Summary of Adverse Events (Blinded Phase) Safety Population
- 10. Table [TAE02a] Number (%) of Subjects with Adverse Events by Body System and Preferred Term (Blinded Phase) – Safety Population
- 11. Table [TAE03a] Number (%) of Subjects with Serious Adverse Events by Body System and Preferred Term (Blinded Phase) Safety Population
- 12. Table [TAE04a] Number (%) of Subjects with Severe Adverse Events by Body System and Preferred Term (Blinded Phase) Safety Population
- 13. Table [TAE05a] Number (%) of Subjects with Study Agent Related Adverse Events by Body System and Preferred Term (Blinded Phase) Safety Population
- 14. Table [TAE06a] Number (%) of Subjects with Adverse Events by Preferred Term and Overall Frequency (Blinded Phase) Safety Population
- 15. Table [TVS01a] Summary of Vital Signs and Change from Baseline (Blinded Phase) Safety Population
- 16. Table [TPE01a] Summary of Physical Examination (Blinded Phase) Safety Population
- 17. Table [TLB01a] Summary of Laboratory (Hematology) Test Results Safety Population
- 18. Table [TLB02a] Summary of Laboratory (Blood Chemistry) Test Results Safety Population
- 19. Table [TLB03a] Summary of Urine Pregnancy Test Results (Blinded Phase) Safety Population

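### Hematology and chemistry are planned only as continuous summaries; outside the AE tables, no SAP text or table title counts women with out-of-range results by arm

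*SAP*

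**What the plan says.** SAP 2.2.2 gives its eighth secondary endpoint as "Incidence and severity of AEs and laboratory values".

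For hematology and chemistry, SAP 3.3.1 (Laboratory Tests) has a single entry: "Laboratory data (haematology and blood chemistry) will be summarized for baseline, post baseline, and change from baseline". SAP 3.1 fixes the content of such a summary: "Continuous variables will be presented by descriptive statistics: n, mean, standard deviation, median, minimum, and maximum". SAP 3.1 also says "Categorical variables will be tabulated by frequency count and percentage", but no categorical laboratory variable is defined anywhere in the SAP text.

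The planned outputs match. SAP 4.1.2 lists "Table [TLB01a] Summary of Laboratory (Hematology) Test Results" and the chemistry counterpart TLB02a. SAP 5.1.2 lists TLB01b and TLB02b for the open-label phase. All four titles describe a summary of results. Individual results are listed in LAB01a, LAB02a, LAB01b and LAB02b.

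The next entry in SAP 3.3.1 treats other safety data differently: "Vital sign and physical exam abnormalities will be summarized". SAP 3.7 supports it with a block of limits headed "Normal Ranges for Vital Signs". For the laboratory analytes, SAP 3.7 gives names only.

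Protocol 8.5 says "The Investigator will assess all abnormal lab values for clinical significance". Values categorised as AEs then enter the AE data.

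**The concern.** Incidence requires a count of women, and severity requires a grade or a threshold. A table of continuous statistics gives neither. If endpoint 8 covers laboratory abnormalities, its only by-arm source is the AE tables, and those depend on what each investigator chose to record.

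This matters more than it would in a trial that had run to plan. The study stopped early. SAP 3.3.2 plans no efficacy analysis for the report, and SAP 3.8 makes safety and PK/PD its focus. The study dose is 8 mg/day, while Protocol 2.2 describes earlier experience up to 4 mg/day, so this is twice the highest dose reported there. Protocol secondary objective 4 presents the blood count, chemistry and liver tests as toxicity assessments. Laboratory toxicity may affect a few women rather than shift a whole arm, and a by-arm count is the usual way to see that.

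SAP 3.8 also merges end-of-study visits into the nominal Week 52, so women with very different exposure share one visit summary. A worst-post-baseline count does not depend on that visit label, although follow-up time would still differ between women.

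**Working it through.** This is mainly a comparison of text. The plan states no figure to reproduce on this point.

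**Step 1. Treatment of each type of safety data**

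| Data | Summary planned in SAP 3.3.1 | Limits given in SAP 3.7 | Count of women by arm |
|---|---|---|---|
| Adverse events | By system organ class and preferred term; severe, serious and drug-related tables | Not needed | Yes (TAE tables) |
| Vital signs | Abnormalities summarised | Yes | Planned in text |
| Physical examination | Abnormalities summarised | Not needed | Planned in text |
| Hematology, chemistry | Baseline, post-baseline, change | None | None in text or titles |

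**Step 2. What reaches the AE tables**

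Protocol 8.2 makes a laboratory change a possible AE if it is judged clinically significant, meaning that it needs action or that the investigator considers it beyond normal physiological fluctuation. Where a diagnosis explains the value, only the diagnosis is reported. The AE tables therefore contain a subset of abnormal results, selected by judgement at about 25 sites (Protocol 4.0) and not by a common threshold. A value subsumed under a diagnosis is counted under that diagnosis, not as a laboratory finding.

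**Step 3. What continuous statistics can and cannot show (illustration)**

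Inputs: arm size 181, the planned evaluable number on BHR-700 (Protocol synopsis; SAP 1.2). Assumed, not in the documents: k women have an ALT rise of 100 U/L and all others have no change. SAP 1.3 says that fewer subjects were enrolled than planned, so an assumed arm of 90 is shown as well.

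Mean change = k × 100 / n. SD of change = 100 × √[(k/n)(1 − k/n)].

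| n | k | Mean change (U/L) | SD | Median | Maximum |
|---|---|---|---|---|---|
| 181 | 1 | 100/181 = 0.6 | 7.4 | 0 | 100 |
| 181 | 4 | 400/181 = 2.2 | 14.7 | 0 | 100 |
| 90 | 1 | 100/90 = 1.1 | 10.5 | 0 | 100 |
| 90 | 4 | 400/90 = 4.4 | 20.6 | 0 | 100 |

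The maximum reveals that an extreme value occurred, but it is the same for one woman as for four. The SD does differ here, because the example sets everyone else's change to exactly zero. With ordinary variation added, the SD could not be turned back into a count. The table shows that the number of women affected is not reported. It does not show that a signal would go unseen.

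**The case against.** The strongest objection concerns endpoint 8 itself. Its wording can be read as two items: incidence and severity of AEs, and, separately, laboratory values. The protocol supports that reading. Its synopsis endpoint on incidence and severity names AEs only, and Protocol 9.1 promises laboratory parameters in descriptive form as a separate bullet. On that reading SAP 3.3.1 delivers what was promised and no endpoint is left without an analysis. This stands as a possible reading, so the point should not be put as a broken commitment. It does not remove the gap, because a shift table is itself descriptive.

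Three stronger inferences are tempting, and the documents do not support them:

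- **That only means and mean changes will be shown.** SAP 3.1 also plans SD, median, minimum and maximum, so an extreme value would be visible.
- **That no table counts any woman with an abnormal result.** Those whose result was recorded as an AE, or under a diagnosis, are counted in the AE tables, which include a severe-AE table. The listings also show every individual hematology and chemistry result.
- **That the laboratory tables contain no abnormality column.** The shells attached to the SAP were not available for this check, and a title that mentions only results does not exclude such a column. The claim is limited to the SAP text and table titles. SAP 4.1 does describe template content as an example only, so a shell column would not replace a stated rule.

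It is also fair to say that a brief report after early termination justifies a lighter set of outputs. That limits the weight of the point. But safety is what that report will be about.

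**Conclusion.** The point holds as a gap in specification. SAP text and table titles plan only continuous summaries of hematology and chemistry, while abnormalities are summarised for vital signs and physical examination. By-arm incidence and severity of laboratory abnormalities would be available only through investigator-recorded AEs.

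The size is modest. No hypothesis test, error rate or sample size is affected, and the underlying data are collected and listed. A reader might infer that liver or hematologic toxicity would be hidden. The documents do not support that, given the maximum, the listings and the AE route. What would be missing is the number of women affected, by arm and against a common threshold.

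The conclusion assumes that the table shells add no out-of-range counts. The 4-of-181 figure is an illustration based on the planned evaluable number and invented rises; the actual arm will be smaller.

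**What to change.** In SAP 3.3.1 (Laboratory Tests), add for each hematology and chemistry analyte, in each phase and by arm:

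1. A shift table from baseline to worst post-baseline value, classed low, normal or high against the central-laboratory range.
2. n (%) newly below and newly above range. The denominator should be women in range at baseline with at least one post-baseline value. Women already out of range at baseline belong in their own shift rows; including them in the denominator would dilute the incidence.
3. For ALT, AST, alkaline phosphatase and bilirubin, counts of women by multiples of the upper limit of normal.

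State which pre-dose value serves as baseline, because SAP 3.7 admits any value from Day 1 or before the first dose and these tests are drawn at both screening and Day 1. Add the new tables to SAP 4.1.2 and 5.1.2. Also reword endpoint 8 so that it is clear whether incidence and severity apply to laboratory values. If the shells already contain these counts, it is enough to state the rule in 3.3.1.

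Cost: one or two extra descriptive tables from existing central-laboratory data, with no change to study conduct.

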#### **Secondary Outcome Measures:**

- Comparison of the reduction in breast density as calculated with the Volpara method and the Cumulus method.
- Laboratory parameters will be summarized in a descriptive fashion.
- Incidence and severity of AEs will be compared between BHR-700 gel and placebo.

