#### 3.6 **Pharmacodynamic and Pharmacokinetic (PD/PK) Data**

- Bone biomarkers (CTx and BSAP) level and change from baseline will be summarized by visit and treatment group. Individual data listing will also be provided.
- Plasma concentration of study agent (4-OHT E&Z isomers) will be summarized by visit and treatment group. Individual data listing will also be provided.
- Hormones (FSH, Estradiol and Estrone) will be summarized by visit and treatment group. Individual data listing will also be provided.
- Coagulation parameters (Protein C Activity, Protein C antigen, Protein S antigen total, Protein S antigen free, Antithrombin III antigen, Activated protein C resistance) will be summarized by visit and treatment group. Individual data listing will be provided as well.

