#### 3.8 Change to Planned Protocol Analysis

Since the study was early terminated, many subjects did not have visit of End of Blinded Phase at week 52. The current nominal Visit of "Week 52" will include both "Week 52" and "End of Study" (EOS). No imputation will be done for the missing data.

Since the study was terminated early, a brief clinical study report will be planned for this study and will focus on the safety and PK/PD results, where PK/PD results of blind phase will be reported only. The baseline characters, safety data and PK/PD data will be reported in the study report.

However, mammographic efficacy data may be analyzed appropriately as ad-hoc analyses after carefully reviewed data. The results of ad-hoc analyses will be reported separately.

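### The lipid and bone-marker secondary endpoints get per-arm descriptive summaries only: no BHR-700 minus placebo difference with an interval is planned, and neither baseline nor the menopausal stratum is used

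*SAP*

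**What the plan says.** SAP 2.2.2 lists as secondary endpoints the changes in total cholesterol, triglycerides, HDL and LDL, and "Change in serum concentration of select bone biomarkers CTx and BSAP".

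The planned analyses are as follows.

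- **Lipids.** They belong to the blood chemistry panel (SAP 3.7; Table TLB02a). SAP 3.3.1, Laboratory Tests: "Laboratory data (haematology and blood chemistry) will be summarized for baseline, post baseline, and change from baseline".
- **Bone markers.** SAP 3.6 (Table TBB01a): "Bone biomarkers (CTx and BSAP) level and change from baseline will be summarized by visit and treatment group".
- **Statistics shown.** SAP 3.1, by treatment group and time point: "Continuous variables will be presented by descriptive statistics: n, mean, standard deviation, median, minimum, and maximum".
- **Intervals.** SAP 3.1 adds that, where appropriate, "all confidence intervals will be two-sided 95% confidence intervals". No section applies this to a lipid or bone-marker difference.
- **Missing values and visits.** SAP 3.8 puts End of Study values under the nominal Week 52 visit and then says: "No imputation will be done for the missing data".

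Randomisation is 2:1 within pre/peri- and postmenopausal groups (SAP 1.2), but no analysis in the SAP uses that factor.

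The descriptive approach is openly stated. Protocol 9.1 has "Laboratory parameters will be summarized in a descriptive fashion", and SAP 1.3 moves the emphasis from hypothesis testing to description because the trial was terminated early.

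**The concern.** Randomisation allows a direct estimate of the drug's effect on these endpoints. The plan stops one step short of it by tabulating the two arms side by side and leaving the comparison to the reader. SAP 3.8 narrows the report to safety and PK/PD results, so these tables are now among its main content.

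Two things are lost. First, no difference is displayed with its uncertainty, so in a reduced sample a reader will compare two means by eye. Second, the baseline value and the menopausal stratum, both scheduled to be collected before dosing, are not used to sharpen the comparison. The baseline- and stratum-adjusted difference cannot be recovered from the summary tables.

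**Working it through.** **The plan's own figure.** The only power statement (SAP 2.3) concerns breast density: difference 6 − 2 = 4, SD 8, two-sided alpha 0.01, 90% power, 272 evaluable women (181:91). It reproduces. The normal approximation gives 90 placebo and 270 in total. Power at 181:91 is 90.6% by the normal approximation and 90.2% by the noncentral t. It says nothing about lipids or bone markers, for which the documents give no SD, correlation or target difference.

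**Baseline adjustment.** Let r be the correlation between baseline and follow-up, with equal SDs at both times and the same r in both arms (assumptions). In units of the outcome variance times (1/n₁ + 1/n₂), the variance of the arm difference is:

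- raw change: 2(1 − r)
- ANCOVA with baseline: 1 − r²
- ratio: (1 − r²) / [2(1 − r)] = (1 + r)/2

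| r (assumed) | variance ratio | variance reduction | SE reduction | equivalent extra women |
|---|---|---|---|---|
| 0.5 | 0.75 | 25% | 1 − √0.75 = 13% | 1/0.75 − 1 = 33% |
| 0.7 | 0.85 | 15% | 1 − √0.85 = 8% | 1/0.85 − 1 = 18% |
| 0.8 | 0.90 | 10% | 1 − √0.90 = 5% | 1/0.90 − 1 = 11% |

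The 95% CI half-width, in outcome SDs, is 1.96 × √(1/181 + 1/91) × √(variance factor), and 1.96 × √(1/181 + 1/91) = 0.252.

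- Planned size, r = 0.5: raw change 0.252, ANCOVA 0.218.
- Planned size, r = 0.7: raw change 0.195, ANCOVA 0.180.
- Half the planned size (90:45, assumed), r = 0.5: raw change 0.358, ANCOVA 0.310.

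Any further gain from the menopausal stratum cannot be computed from the documents.

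**Repeated measures (lipids only).** Lipids are drawn at Weeks 26 and 52 (Protocol Appendix 1), so a joint model could borrow from Week 26 for women without a Week 52 value. With a fraction m lacking Week 52, the variance of the Week 52 arm mean relative to observed cases is [(1 − ρ²)/(1 − m) + ρ²](1 − m) = 1 − mρ². Here ρ is the Week 26–Week 52 correlation that remains after baseline adjustment. If all pairwise correlations equal r (assumption), ρ = r/(1 + r).

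| m (assumed) | r (assumed) | ρ | further variance reduction, mρ² |
|---|---|---|---|
| 0.3 | 0.5 | 0.33 | 3% |
| 0.5 | 0.7 | 0.41 | 8% |
| 0.5 | 0.8 | 0.44 | 10% |

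Using r itself in place of ρ would give 8%, 25% and 32% for these rows. That would count the baseline information twice once baseline is in the model.

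**The visit definition.** SAP 3.8 merges End of Study into nominal Week 52. Protocol 5.4 asks for final evaluations when drug is stopped, and the Week 52/End of Study visit in Protocol 7.3 includes chemistry and bone markers. A woman stopped by termination may therefore have a value in the Week 52 row, taken after a shorter exposure.

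**The case against.** The strongest reply is that this is a disclosed choice. The protocol planned descriptive laboratory summaries from the start, the SAP gives early termination as its reason for emphasising description, and no passage contradicts another. That stands: this is a missed opportunity, not an inconsistency. It does not count against the addition, because a difference with an interval and no p-value is estimation and fits both documents.

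Four stronger readings are tempting, and the documents do not support them.

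- **That the report would hold no information on the treatment effect.** Change from baseline is summarised with n, mean and SD by arm, so a crude difference and its interval can be derived. Subject-level listings of randomisation, chemistry and bone markers are also planned (SAP 4.2). What is absent is a planned and displayed difference, and any adjusted one.
- **That women cut off by termination drop out of the Week 52 row.** End of Study values are placed there. The documents give no missing fraction, so 30% to 50% is only an illustration.
- **That these endpoints carry the case for low systemic effect.** Protocol 2.2 rests that case on lower systemic 4-OHT levels, on endocrine and coagulation parameters, and on named risks of oral tamoxifen. Lipids and bone markers are not among them, although the synopsis lists bone biomarkers as a safety parameter.
- **That baseline is available for every woman.** Sampling is scheduled, but completeness is not stated.

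The gain in precision is also modest, and adjustment does not restore lost women or lost follow-up.

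**Conclusion.** The point holds as a gap in estimation. For the lipid, CTx and BSAP endpoints the SAP plans no BHR-700 minus placebo difference, no interval, and no use of baseline or the randomisation stratum.

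The larger benefit is a pre-specified, displayed comparison with its uncertainty. The gain in precision over raw change is secondary: variance 25% to 10% lower for r between 0.5 and 0.8, which is assumed because the documents give no value. A repeated-measures model would add about 3% to 10% for lipids, under equal correlations and an assumed 30% to 50% missing.

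Adjustment does not cure the pooled visit. A model fitted to nominal Week 52 as defined in SAP 3.8 would put a precise-looking interval on a mixture of treatment durations, so the visit must be separated first.

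**What to change.** Add to SAP 3.3.1 (Laboratory Tests) and 3.6, for the blinded phase:

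1. Keep all per-arm descriptive columns.
2. For total cholesterol, HDL, LDL and triglycerides (TLB02a), report the BHR-700 minus placebo difference in change from baseline with a 95% CI at Week 26 and at Week 52. Use ANCOVA with baseline value and menopausal stratum.
3. For CTx and BSAP (TBB01a), report the same at Week 52.
4. Give no p-values.
5. Base the Week 52 estimate on true Week 52 visits. Report the pooled Week 52/End of Study visit as a separate estimate, labelled as mixing treatment durations. Show the number of women per arm in each.
6. Optionally, for lipids, use a repeated-measures model with baseline, stratum, treatment, visit and treatment-by-visit. It imputes nothing, so it fits SAP 3.8.

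The cost is a few lines of SAP text and minor extra programming on samples already scheduled. The true Week 52 estimate uses fewer women and describes those who reached that visit. The repeated-measures option assumes data missing at random. That is plausible where the sponsor's termination is the cause, and less certain where a woman withdrew for her own reasons.
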